### **Surgical Technique**

Surgical implantation of DBS leads will be carried out employing techniques previously reported ([name], [name] et al. 1997) ([name], [name] et al. 1996) as described below. Patients will have antiparkinsonian medication withheld for 12-48 hours prior to surgery. During this time, patients will be constantly accompanied by a caregiver to insure their safety.

After application of a stereotactic headframe under IV sedation in the operating room to maximize patient comfort, MR imaging is performed using a 1.5-T magnet (General Electric, Milwaukee, WI). The MRI scanner in our facility is located adjacent to the operating room. Images are acquired using a 3-D volumetric spoiled GRASS sequence in the sagittal and axial planes. The sagittal acquisition is a 2 cm volume of 1 mm thick contiguous slices obtained in 3 minutes. This sequence will be used to define the anterior (AC) and posterior (PC) commissures. The second acquisition uses an identical sequence in the axial plane consisting of a 12 cm volume of 1mm thick contiguous slices obtained in 10 minutes. This sequence will be used to construct multiplanar (axial, sagittal, and coronal) viewing of the target point and trajectory. Axial images are used because this data is least vulnerable to any magnetic distortion. Additionally, a directly acquired axial fast spin echo inversion recovery sequence

(T1=200, TR=2200, TE=24, slice thickness=2mm) is obtained. This sequence is used to construct coronal images for direct visualization of the subthalamic nucleus (STN) and substantia nigra (SN). Targeting of the fornix/hypothalamus will take place utilizing the same computer software/imaging.

MR accuracy is verified by weekly quality assurance evaluations of the MR magnet using stereotactic phantoms. MR data is transferred over a network directly to the stereotactic planning computer in the OR computer room. The COMPASS software is used to define the AC and PC, the AC-PC line, and its midpoint.

The initial target is chosen using standard coordinates for the STN (3 mm posterior, 4 mm inferior, and 12 mm lateral to the midpoint of the AC-PC line). Final anatomic target adjustments are made based on correlation with the visualization of both SN and STN on the T2 weighted coronal images. A trajectory is chosen to include the target site, the midpoint of the AC-PC line and to avoid the lateral ventricles.

Microelectrode recording (MER) is then performed to verify the borders of the STN. STN has a characteristic electrophysiological activity that may be recognized by the discharge pattern within high background noise. The background noise diminishes distinctly at the inferior border of the STN into the SNR. Single units are recorded, both in the STN and SNR. In STN, cells fire with high activity (50-60 Hz), the spikes being almost symmetrical. They may respond to passive movements of the limbs with an increased firing rate. Cells in SNR typically produce larger potentials with slower firing rates (15-20Hz) and are irregular. They may be less likely to vary with limb movement. The medial and lateral borders of the STN formed by the lemniscal and corticospinal fibers respectively are identified by microstimulation-evoked sensory and motor responses. The MERs are again correlated to the tri-planar MR anatomy in the COMPASS software to assist in verification of the borders of the STN. We will perform MER using 1-5 microelectrodes placed simultaneously with our linear array (separated 3 mm apart center-to-center) aligned with the long axis of the STN as judged by its location immediately superior to SNR.

Microstimulation (0.5-5 uA, 130 Hz, 60usec pulse width) is carried out over the length of the STN to determine clinical response based on measurement of rigidity at the contralateral wrist to passive movement, as well as bradykinesia. Additionally, increasing microstimulation-induced side effects (such as paresthesias, vertigo, diplopia, eye deviation, etc.) are determined at each level. The final target will be determined by selecting the microelectrode track with the largest inferior-superior span of STN recording, the optimal clinical response in terms of reduction of rigidity and the highest threshold for side effects (particularly eye deviation and diplopia).

After the final STN target is selected, a Medtronic or Boston Scientific multipolar electrode is stereotactically placed at the target site and macroelectrode stimulation is performed. Adjustments in the final electrode placement are made based upon clinical response of parkinsonian symptoms and sensory and motor thresholds, selecting the

location that provides the greatest reduction in parkinsonian signs without significant side effects.

The initial electrode will be placed on the appropriate side contralateral to the most severe symptoms, or the dominant hand. If stimulation demonstrates improvement in parkinsonian symptoms at acceptable thresholds, the electrode will be secured in the burr hold and placed in a subgaleal pocket. Immediately thereafter, the hypothalamic electrode will be placed, with similar stimulation being employed to confirm proper placement.

Both hemispheric electrodes will subsequently be joined to extension leads which will be connected to an ipsilateral IPG placed in an infraclavicular superficial location.

### **Follow-Up**

All patients will be seen preoperatively and at, 3, , 12, , 24months, and yearly intervals in order to adjust medications and stimulation parameters optimally. MRI scanning will be completed at baseline, and at yearly follow up visits. During year 4 and 5 a member of the study team will call the patient to see if they require additional evaluations.

Evaluations will be performed as outlined in the Summary – Evaluation Protocol table.

We will attempt to optimize the use of antiparkinsonian medications following surgery in conjunction with DBS parameters. Patients will be seen up to daily within the first week post-operatively for such adjustments and for suture removal.

### **Data Handling**

Data obtained from all evaluations will be recorded on electronic data sheets or in Epic by the principal investigator ([name]) and study coordinator ([name]);

### **Brain Bank Registry**

Clinicopathological studies in individuals who have undergone BSUBSTIM may be extremely informative and every attempt will be made to obtain autopsy in the unlikely event of death during the study. All patients in the study will be strongly encouraged to participate in the registry although this participation is not mandatory.

### Motor Function Testing

#### Evaluations

Patients' motor function will be evaluated pre-operatively and at, 312, 24months, and yearly thereafter with quantitative outcome measures, employing standardized motor rating scales as have been previously reported by the investigators. ([name], [name] et al. 1997) Changes in motor function of both sides of the body will be quantitated. Gait assessments may be videotaped if patient agrees, but it is not required.

#### Motor Function Testing – Drug and Stimulation Profile

During all post-operative visitspatients will be seen “ON” stimulation and “ON” medication. Time of last dose of antiparkinsonian medication will be collected.

The following motor function testing battery consists of: modified UPDRS, modified Hoehn & Yahr (Hoehn and Yahr 1967) scoring.

The motor function tests will be scored while patient is adhering to normal medication schedule and optimal “on” DBS settings.

#### Neuropsychological testing

A short test of mental status utilizing the Kokmen test will be completed on patients at 3 month follow up. The full neuropsychological test battery (see below) will be administered at baseline, and at yearly follow-up evaluations. Per normal clinical care

Testing will take place annually (within 6-month windows of the exact date).

Post-operative testing will be completed with the patient in an “ON” setting.

#### Assessment and Statistical Analyses

The primary method of assessing treatment effects will be paired t-tests at the various post-operative intervals.

The primary efficacy parameters are neuropsychological battery scores over time in comparison with pre-operative scoring.

Secondary efficacy parameters will include UPDRS scoring (motor and activity of daily living subscores).

The primary endpoints will be the change in neuropsychological scoring from baseline to 12 and 36 months, expressed as a percentage change from baseline (employing “on”/“on” post-operative status versus “on” pre-operative values. Two-sided two-sample t-tests will compare post-operative changes to pre-operative data. Such

comparisons will take place when the full contingent of patients are accrued and have completed such assessments.

The effect of stimulation on cognitive functioning and mood state will be assessed using t-tests for dependent samples to compare performance on neuropsychological tests and POMS scores in the “on” and “off” condition at each follow-up evaluation. Changes in cognitive functioning, mood, and HRQOL from presurgical baseline will be analyzed using repeated-measures ANOVAs, with neuropsychological test scores as the DV and time of testing as the repeated measure. Demographic variables and measures of social support and locus of control will be entered into analyses of covariance whenever appropriate.

Hierarchical multiple regression analyses will be used to determine the relationship between presurgical psychosocial and neuropsychological variables and postsurgical outcome, as measured by HRQOL.

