### Tandem Deep Brain Stimulation for Parkinson's Disease

Deep brain stimulation (DBS) targets for Parkinson's disease (PD) have been limited to neuronal regions wherein lesions have produced beneficial effects. Every DBS target routinely employed at international centers: ventral intermediate nucleus of the thalamus, subthalamic nucleus, or globus pallidus internus, have been historically lesioned with documentation of ensuing motor benefit. The positive ramifications have included predominantly improvement in motor function and functional "on" time. Patients undergoing surgery have been highly selected; PD patients with depression and dementia have consistently been avoided as surgical candidates [1].

While most series of DBS surgery for PD patients find minimal changes in cognition within the first year following surgery, longitudinal series subsequently document that cognitive decline and dementia are still commonplace. Additionally, most DBS series have avoided operating on elderly PD patients who are at most risk for dementia. We

have suggested for some time that unilateral STN-DBS be routinely employed (as opposed to immediate bilateral surgery) in PD, as it may be therapeutically effective and carry fewer cognitive complications, particularly in elderly patients [2].

Most long-term follow-up indicate that speech, axial motor features and cognitive decline frequently become apparent in PD patients receiving DBS [3]. Studies examining specific cognitive outcomes more than two years after surgery indicate that the majority of STN-DBS patients demonstrate significant declines in nonverbal memory, semantic fluency, and processing speed, with the same percentage converting to dementia as those PD who were not surgical patients [4]. Hence, there is no evidence to suggest that current DBS targets, even employed in a selected, non-demented, non-depressed cohort, subsequently minimize the risk for future dementia.

In summary, currently available pharmacological and surgical therapies do not consistently, effectively ameliorate balance and cognitive decline/dementia or reduce their risk, and frequently exacerbate these problems in the short-term.

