#### Could DBS potentially impact cognitive decline/dementia in PD?

DBS with high-frequency stimulation of the limbic circuitry, namely the anterior thalamic nuclei, demonstrates neurogenesis of neurons in the dentate gyrus of the hippocampus, a component of the limbic circuit.

The ability to produce adult hippocampal neurogenesis has also been associated with effective antidepressant treatments. Studies in mice have demonstrated that stimulation of the ATN may produce increases in neural progenitors in the dentate gyrus of the same variety that can be stimulated by fluoxetine and physical exercise [8]. This suggests that ATN stimulation might be useful for limbic circuitry activation and influence on cognition and mood. While most clinical studies in PD patients do not suggest that cognition is negatively impacted by DBS per se, this may also be possible. DBS of the anterior thalamus at high current has shown the ability to impair memory in rat animal models [9].

An anecdotal report concerning DBS in the fornix and hypothalamus in a patient being treated for obesity included descriptions of impressive memory enhancement [10]. While on the operating table, this patient was able to provide detailed memory recollections from 30 years previous. Subsequent evaluation disclosed that there were EEG effects in the hippocampal formation and medial temporal lobe in conjunction with high-intensity stimulation (3-5 V, 60-microsecond pw, 130 Hz). Additionally, performance on neuropsychological testing after chronic hypothalamic stimulation demonstrated improvements in attention, verbal learning (short- and long-delay recall) and spatial associative learning. This testing suggested that hypothalamic stimulation induced enhanced recollection in the memory process. The mechanism thought to be responsible was driving activity of the hippocampal memory circuit through stimulation of the fornix. The fornix represents the major axonal bundle from the hippocampus and medial temporal lobe. Lesions in the fornix are also well known to produce memory deficits in humans. In contrast in this instance, apparent driving of activity in the ipsilateral medial temporal lobe to unilateral hypothalamic stimulation (“on” state), was associated with increased memory ability.

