A subsequent trial has ensued examining the impact of DBS on memory circuits in Alzheimer’s disease (AD) [11]. This trial recruited six patients with early AD. All had Clinical Dementia Rating scores of 0.5 or 1.0 [12] and scores between 15-26 on the Mini Mental State Examination (MMSE)[13]. Each were implanted bilaterally in the vertical portion of the fornix within the hypothalamus. Assessments with the Alzheimer’s Disease Assessment Scale, Cognitive Subscale (ADAS-Cog)[14] took place at baseline and 6 and 12-months post-operatively. After 6 months of stimulation, 4 of 6 patients showed improvement, with lowering of 1.3-4.0 points in the ADAS-Cog scores. This magnitude compares favorably to the reported impact of donepezil in mild cognitive impairment, which is 0.5 points [15].

After 12 months, one patient had 4.4 points lower than baseline, 2 patients a 2-point increase, 1 patient a 5-point increase, and 2 patients >5 point increases. The expected change in the cohort of 6 was: 2 patients had less than expected increases, 1 more, and 3 within the expected range. Interestingly the patient with the greatest improvement experienced the most vivid experiential experience with stimulation during surgery, as had been the case with the original anectodal patient reported. Functional imaging carried out in this trial also suggested that fornix/hypothalamic-DBS produced changes in the

cognitive and limbic brain areas (improved glucose metabolism), were the basis for observed changes in some of the AD patients. These authors also suggest that DBS may drive greater delivery of neurotrophin brain-derived neurotrophic factor and influence neurogenesis in the diseased hippocampus.

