### **Scientific basis or justification**

Parkinson's disease is a common neurodegenerative disorder with no treatment that definitively alters the natural progression of the condition. With progression of symptoms, patients with Parkinson's disease (PD) frequently develop significant disability despite optimal medical therapy. This study is designed to test a new technology for the treatment of severe PD.

Currently available surgical treatments, such as pallidotomy, GPi-DBS, and STN-DBS, offer some benefit for selected patients but do not influence cognitive dysfunction. Reports concerning cognitive benefit have documented potential improvement with

placement of DBS electrodes and stimulation in the fornix/hypothalamus in normal and patients with mild Alzheimer's disease.

We propose a pilot study of tandem DBS in 12 PD patients experiencing disability despite optimal medical therapy. The subthalamic nucleus and substantia nigra reticulata are crucial output nuclei in the cortico-basal ganglia-thalamic anatomy in which abnormal physiological activity have been described in animal models of parkinsonism and confirmed in human PD. DBS of STN bilaterally has been shown to ameliorate parkinsonism in both settings. The substantia nigra reticulata is an output nucleus that shares neurophysiological function with the internal segment of the globus pallidus or medial pallidum. Lesioning or DBS of the medial pallidum have both been shown to improve parkinsonism in animal models and human parkinsonism. We believe that DBS of both STN and hypothalamus would prove optimal in terms of reducing both parkinsonian and cognitive signs and symptoms.

Our surgical technique (MRI-microelectrode-guided procedure) allows for the implantation of bihemispheric DBS leads and pulse generator within the space of 3 hours.

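### Change in cognition is analysed only through group means, so with 12 patients a marked decline confined to a few would very probably give a non-significant result; per-patient changes should be listed and decliners counted

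*Combined protocol and SAP*

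**What the plan says.** The study is small and has no control group: "We propose a pilot study of tandem DBS in 12 PD patients experiencing disability despite optimal medical therapy". Under Assessment and Statistical Analyses the main method is given as "The primary method of assessing treatment effects will be paired t-tests at the various post-operative intervals", and Statistical method/rationale repeats it. The endpoint is defined thus: "The primary endpoints will be the change in neuropsychological scoring from baseline to 12 and 36 months, expressed as a percentage change from baseline". The same section adds a second description of the test, "Two-sided two-sample t-tests will compare post-operative changes to pre-operative data", and says that changes in cognition, mood and quality of life from baseline "will be analyzed using repeated-measures ANOVAs, with neuropsychological test scores as the DV and time of testing as the repeated measure". It also plans dependent-sample t-tests of stimulation on against off, covariance analyses, and a hierarchical regression whose outcome is quality of life.

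Neuropsychological testing provides the full battery at baseline and at each yearly visit, so a change score can be computed for every patient tested. The Hypothesis in the Summary claims both safety and effectiveness, for cognitive as well as motor dysfunction.

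The background treats cognitive decline as a real possibility. It reports that after STN-DBS "the majority of STN-DBS patients demonstrate significant declines in nonverbal memory, semantic fluency, and processing speed", and that "DBS of the anterior thalamus at high current has shown the ability to impair memory in rat animal models". It describes the cited fornix-DBS trial in six Alzheimer's patients one patient at a time, and compares their 12-month change with what was expected: "2 patients had less than expected increases, 1 more, and 3 within the expected range".

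**The concern.** The t-tests and ANOVAs ask whether the average patient changed. A second question, whether some patients lost ground, is not asked by any planned analysis. No section sets a limit for individual decline, counts decliners, or takes conversion to dementia as an analysed result.

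In a pilot of a new target this second question matters. If stimulation harms a minority, the mean moves little, and the decliners also widen the SD in the denominator of the t statistic. The primary analysis could then be non-significant while two or three of 12 patients have clearly declined on a test. The scores that would show this are already being collected.

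**Working it through.** **Inputs.** n = 12 and a two-sided test come from the document. The plan gives no alpha, SD of change, target effect or power, so there is no stated figure to reproduce. I assume alpha = 0.05 and measure change in units of the SD of within-patient change (noise SD = 1).

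**What the t-test needs.** The critical value on 11 df is 2.201. The observed mean change must be at least 2.201/√12 = 0.64 SD. For 80% power the true mean change must be 0.89 SD.

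**Why a few decliners are missed.** Let k of 12 patients decline by d and the rest stay at 0.

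- Mean change = −kd/12.
- Expected variance of the changes = 1 + d²·k(12−k)/(12·11).
- k = 3, d = 2: mean −0.50; variance 1 + 4·27/132 = 1.82, SD 1.35; t ≈ −0.50/(1.35/√12) = −1.28.
- k = 3, d = 3: mean −0.75; variance 1 + 9·27/132 = 2.84, SD 1.69; t ≈ −1.54.
- With no noise, |t| = √(11k/(12−k)) whatever the size of d. This gives p = 0.34 (k = 1), 0.17 (k = 2), 0.082 (k = 3) and 0.039 (k = 4).

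So with three decliners, larger individual harm hardly helps: t tends to −1.91, short of −2.20.

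**Simulation with noise (200,000 trials per row), other patients unchanged.**

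| True decliners | Size of decline | t-test shows significant decline |
|---|---|---|
| 3 of 12 | 2 SD | 15% |
| 3 of 12 | 3 SD | 18% |
| 6 of 12 | 3 SD | 84% |
| 7 of 12 | 1.5 SD | 61% |
| 7 of 12 | 2 SD | 79% |

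For declines of 2 to 4 SD, the chance of a non-significant test is 95–97% with one decliner, 92–93% with two, 81–85% with three and 57–74% with four. If the other nine gain 0.2 to 0.3 SD, three decliners are missed in 93–97% of trials.

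**What a count adds.** Take an illustrative cut-off of −1.645 SD of change (5% per patient by chance, SD known). On one test, noise alone gives at least one flag in 1 − 0.95¹² = 46% of trials and at least three in 2.0%. With three true decliners, at least three are flagged in 44% of trials (2 SD) or 84% (3 SD). That beats 15% and 18%, but at 2 SD it still misses more often than not.

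**Precision.** Exact 95% intervals for the proportion declining: 0/12, 0 to 26.5%; 1/12, 0.2 to 38.5%; 2/12, 2.1 to 48.4%; 3/12, 5.5 to 57.2%.

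**How the limit is built matters.** At the ideal cut-off, 12 × 0.05 = 0.6 flags are expected by chance. That figure does not carry over to a limit made from the SD of these 12 baselines and a published retest correlation. With published r = 0.8 (assumed) and no true change, simulation gives 0.76 flags if the true r is 0.8 and 1.6 if it is 0.6. In the latter case a 0.3 SD general decline raises it to 2.6.

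**The case against.** **The plan does not say that a null test means no harm.** Correct. A reader might infer that decline in a few patients would be reported as absence of change. The document does not say how a non-significant result will be worded, and it calls the scores efficacy parameters. What can be said is that the mean change would very probably be non-significant.

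**Individual outcomes are not wholly absent.** Logistical Possibilities names dementia status as part of the primary outcome, and the text on risks and consent under Inclusion/Exclusion Criteria sends untoward outcomes to the IRB. However, dementia status never reaches either statistical section, and the IRB sentence has no cognitive criterion.

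**The cited fornix-DBS trial does not show improvers cancelling decliners.** This reading is tempting because one patient was 4.4 points better at 12 months and two were more than 5 worse. But five of six worsened. With the two open-ended values set at 5 to 8 (assumed), the mean worsening is (−4.4 + 2 + 2 + 5 + 10)/6 = 2.4 to (−4.4 + 2 + 2 + 5 + 16)/6 = 3.4 points. That mean moved towards harm. The trial shows that individual responses can differ, and no more. The document also does not say why it was described patient by patient.

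**The STN-DBS background describes a majority declining.** A decline in 7 of 12 would be detected 61 to 79% of the time at 1.5 to 2 SD. The t-test is therefore not blind to cognitive decline in general. The background also says that most clinical studies in Parkinson's disease do not suggest that DBS harms cognition, though that evidence is not about this target.

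**A count has faults of its own.** It is noisy, it multiplies across tests, and without controls it cannot separate fornix stimulation from the STN effect or disease progression. With 10 independent tests (assumed; the battery list is not in the text available) at two visits, 10 × 2 × 0.6 = 12 chance flags would be expected. This stands, and it shapes the fix.

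**Conclusion.** The concern holds as a limited one. Every planned analysis of change in cognition works on group means, and none looks at individual decline. With 3 of 12 patients down 2 to 3 SD and the rest unchanged, the primary test would show a significant decline only 15 to 18% of the time; with one or two decliners, less than 10%. These figures rest on an assumed 5% alpha and on normally distributed change measured in units of its own SD.

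The weakness disappears as decline becomes common, and it does not mean that the mean analysis should be replaced. A per-patient summary would be a worthwhile, low-cost descriptive addition. It would not be a formal test of harm.

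**What to change.** Add to Assessment and Statistical Analyses and to Statistical method/rationale:

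- Individual changes from baseline on each battery test at 12 and 36 months will be listed or plotted.
- For a small set of tests named in advance, the number and proportion of patients declining beyond a pre-specified reliable-change limit will be reported with an exact 95% confidence interval. If all tests are used, their number will be stated so that chance flags can be judged.
- The limit will use the published standard error of the difference for that test, with a correction for practice effects because testing is repeated yearly. It will not use the SD of these 12 baselines. No fixed figure such as 0.6 of 12 will be printed as the number expected by chance.
- Dementia status, already named under Logistical Possibilities, will be reported for each patient.
- The count is descriptive. Without controls it cannot separate harm from stimulation from the STN effect or progression, and 0 of 12 still allows a true rate of up to 26%.
- No claim of cognitive safety will rest on a non-significant mean change.

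The background already cites a study of reliable change indices two years after bilateral STN-DBS (reference 4), which can serve as a descriptive comparison.

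The cost is a few lines of text and a little more analysis on scores already collected, with no new tests or visits. The price is a set of imprecise counts that must be read with care.

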### **Statistical method/rationale**

The primary method of assessing treatment effects will be paired t-tests at the various post-operative intervals.

The primary efficacy parameters are neuropsychological scoring. Secondary measures are UPDRS scoring (motor and activity of daily living subscores) and changes in hippocampal volume as measured on MR imaging.

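### Two unranked primary times (12 and 36 months) with no success rule, alpha or multiplicity rule in the available text, and two conflicting t-tests for the same within-patient comparison

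*Combined protocol and SAP*

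**What the plan says.** The Assessment and Statistical Analyses section defines the primary outcome twice. It first says: "The primary efficacy parameters are neuropsychological battery scores over time in comparison with pre-operative scoring". It then fixes the times: "The primary endpoints will be the change in neuropsychological scoring from baseline to 12 and 36 months, expressed as a percentage change from baseline". The times are not ordered and no success rule is attached to them. In the IRB summary, Statistical method/rationale says only: "The primary efficacy parameters are neuropsychological scoring".

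Two tests are given for the pre-to-post comparison. One sentence reads: "The primary method of assessing treatment effects will be paired t-tests at the various post-operative intervals". A later one reads: "Two-sided two-sample t-tests will compare post-operative changes to pre-operative data". The section also plans repeated-measures ANOVAs of change from the presurgical baseline, and does not say how they relate to the t-tests.

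On timing, the plan says that these "comparisons will take place when the full contingent of patients are accrued and have completed such assessments". No significance level or multiplicity rule appears in the available text.

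The Neuropsychological testing section says: "The full neuropsychological test battery (see below) will be administered at baseline, and at yearly follow-up evaluations". The battery list it points to, and the content of the Evaluation/Data Collection table, are not in the text available here. A lead score may be marked in either place.

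**The concern.** With two primary times and no rule for combining them, the plan does not define what counts as a positive primary result. One analyst could claim success on either time and another could require both, and the error rates of these readings differ several-fold. If several battery scores are primary, the choice widens further.

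The two test names add a second freedom. All 12 patients supply both the pre-operative and the post-operative scores. A two-sample test treats these as independent groups and discards the pairing, so the two tests can give very different p-values on the same data. With 12 patients, a choice of time or test made after seeing results would be hard to detect or correct.

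**Working it through.** The plan states no alpha, power or sample-size derivation, so it has no figure of its own to reproduce.

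**Inputs**
- n = 12, single group, so 11 degrees of freedom for a paired test (Basic study plan).
- Primary times: 12 and 36 months (Assessment and Statistical Analyses).
- Two-sided tests: the plan says so in the two-sample sentence.
- Assumed: 5% per test.
- Assumed: correlation r between the 12- and 36-month changes, from 0 to 0.9. A shared baseline with equal variances and equal correlations gives r = 0.5.
- Assumed: correlation w between pre- and post-operative raw scores, 0.6 to 0.8.

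**Step 1. One score, two times, paired tests, no true change**

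If the two tests were independent:
- either time significant: 1 - 0.95² = 9.75%;
- both times significant: 0.05² = 0.25%;
- a false improvement at either time: 1 - 0.975² = 4.94%.

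Simulation of two correlated paired t-tests (n = 12, 400,000 runs per setting) gives:

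| Success rule | Result |
|---|---|
| Either time, any direction | 9.7% (r = 0), 9.2% (0.5), 9.0% (0.6), 8.5% (0.7), 8.0% (0.8), 7.1% (0.9) |
| Either time, improvement only | 4.9% (r = 0) to 3.6% (r = 0.9) |
| Both times, any direction | about 0.3% (r = 0) to 2.8% (r = 0.9) |

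**Step 2. Paired against two-sample on raw scores**

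With score SD equal to 1, the paired standard error is √(2(1 - w)/12). The two-sample standard error is √(2/12). The two-sample value is therefore too large by a factor of 1/√(1 - w):
- w = 0.6: 1/√0.4 = 1.58;
- w = 0.7: 1/√0.3 = 1.83;
- w = 0.8: 1/√0.2 = 2.24.

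Simulated results for one two-sample test at nominal 5%, with effects in SDs of change:

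| w | False-positive rate | Power at 0.5 SD | Power at 0.8 SD |
|---|---|---|---|
| 0.6 | 0.4% | 10% | 35% |
| 0.7 | 0.2% | 5% | 22% |
| 0.8 | 0.04% | 1.5% | 9% |

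The paired test (noncentral t, noncentrality 0.5 × √12 = 1.73 and 0.8 × √12 = 2.77) has power of 35% and 71%.

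**Step 3. Effect of the fix**

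With one named score and one named time, the error is 5% by construction. With 2.5% at each of two times, it is 1 - 0.975² = 4.9% at r = 0, 4.7% at r = 0.5 and 4.1% at r = 0.8. Paired power then falls from 35% to 24% at 0.5 SD and from 71% to 58% at 0.8 SD.

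**The case against.** The plan never says that success at one time is enough. If both times were required, the one-score error would be below 5% and there would be no inflation. That stands, and it is why the defect is an unstated rule rather than a proven excess. Likewise, a reader might quote a flat 9-10%. That needs the either-time rule, an assumed 5% alpha, the paired test, no true change and a time correlation of about 0.6 or less. It also counts false declines. If patients truly decline, false improvements become rarer still. The background section reports of longer-term follow-up that "the majority of STN-DBS patients demonstrate significant declines in nonverbal memory, semantic fluency, and processing speed".

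A reader might also infer that the plan names no lead score and that a large battery pushes the error far higher. The documents do not support this: the battery list and evaluation table are not in the available text, so neither the absence of a lead score nor the number of scores can be established.

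Another tempting reading is that averaging percentage changes inflates false positives. It does not in general. It can shift the mean upward and lose power for scores with low or widely spread baselines, and matters little otherwise.

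Finally, this is a 12-patient pilot, and waiting for full accrual and assessment limits early looks. Both are fair and lower the weight of the point. Neither ranks the times nor chooses between the tests. The ANOVAs do not settle the matter either, since nothing makes them a precondition for the t-tests.

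**Conclusion.** The point holds in a limited form. Two primary times are unranked, no success rule is stated, and the available text has no alpha or multiplicity rule. For one score the false-positive chance is 7-10% if either time counts and 0.3-2.8% if both must be significant, on the assumptions listed. More primary scores would raise the either-time figure by an unknown amount.

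The conflict between tests needs no battery list to establish. Read as a test on raw pre- and post-operative scores, the two-sample wording is wrong for this design, with a per-test error of about 0.04-0.4% and most of the power lost. Under that reading the plan would be far too conservative, so it cannot simply be called anti-conservative as written.

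All these rates concern change from baseline. With no control group, neither a significant change nor better multiplicity control shows an effect of stimulation, and a reader should not infer one. The point should be corrected, but it does not undermine the study.

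**What to change.** In Assessment and Statistical Analyses:

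- Replace the two-sample wording with the paired t-test.
- Name one primary score, or one composite standardised to norms, and one primary time. Alternatively, test that score at 2.5% at each of 12 and 36 months.
- Make this choice before anyone on the study team reviews post-operative battery scores for the purpose. If scores have already been seen, say so.
- Label the other scores and times, and the repeated-measures ANOVAs of the same changes, as exploratory or supportive, and report estimates with confidence intervals.
- Test absolute change and give percentage change descriptively only (a minor point).
- State that the test concerns change from baseline in a single group, not an effect attributable to stimulation.
- Align Statistical method/rationale in the IRB summary.

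The cost is wording only, with no added visit, test or patient. Domain-specific results would no longer be primary, and a composite would dilute an effect confined to one domain; if such an effect is expected, name that domain's score. Splitting alpha costs the power shown in Step 3 and raises the change detectable with 80% power from 0.89 to 1.01 SD. Naming one time avoids that loss.
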